2.3 Study Day

Study Day is relative to the first dose date of study drugs:

- If analysis date is on/after the date of first dose of study drugs, Study Day = analysis date – treatment start date +1.
- If analysis date is before the date of first dose of study drugs, Study Day = analysis date – treatment start date.

2.4 Study Visits

Study visits in EDC datasets include screen, C1D1, C1D2 C1D8, C2D1, C2D8, C2D15, C3D1, C3D8, C4D1, C5D1, C6D1, C6D15, ..., CnD1, End of Treatment, safety follow ups, survival follow ups as well as unscheduled. The unscheduled study visits will not be recalculated for the analysis by visit, but the unscheduled visit values will be considered in the summary of worst change from baseline.

2.5 Coding Dictionaries

Medical history, medical or surgical procedures, and AEs will be coded using Medical Dictionary for Regulatory Activities (MedDRA) version 27.1.

Confidential

Prior and concomitant medications will be coded using the WHO-Drug Dictionary September 2024 B3.

AEs and laboratory values will be graded with NCI CTCAE 5.0.

2.6 Stratified Analysis

No stratification is planned.

2.7 Testing Hypotheses

Arms I, II, III, IV, and V of the Phase 2a study stage will follow the Simon's two-stage minimax design. A test from the Simon minimax design for null hypothesis ORR proportion 4% vs. alternative hypothesis 21% in the arm population will be conducted in selected arms at 1-sided alpha = 0.025.

2.8 Handling of Missing Data

2.8.1 Handling of Partial Dates for Adverse Events

When determining the treatment-emergent adverse events (TEAEs), partial AE start and/or end dates will be handled as Table 1.

Table 1 Imputation Rules for Adverse Event Partial Dates

Date	Missing Part	Imputation Rule
Start Date	Missing Day	Assign first day of month unless it is the same month and year of the first dose of study drugs. Otherwise, assign date of first dose of study drugs or AE end date (if not missing), whichever is earlier.
	Missing Day, Month	Assign Jan 01 unless the year is year of first dose of study drugs. Otherwise, assign date of first dose of study drugs or AE end date (if not missing), whichever is earlier.
	Missing Day, Month, Year	Assign date of first dose of study drugs or AE end date (if not missing), whichever is earlier.
End Date	Missing Day	Assign the last date of the month or death date or data cut-off date (or end of study date), whichever is earliest.
	Missing Day, Month	Assign Dec 31 or death date or data cut-off date (or end of study date), whichever is earliest.
	Missing Day, Month, Year	If ongoing, end date is missing. Otherwise, assign death date or data cut-off date (or end of study date), whichever is earlier.

2.8.2 Handling of Partial Dates for Medications

When determining if a medication is a prior or concomitant medication, partial start and/or end date will be handled as Table 2.

Table 2 Imputation Rules for Medication Partial Dates

Date	Missing Part	Imputation Rule
Start Date	Missing Day	Assign first day of month unless it is the same month and year of the first dose of study drugs. Otherwise, assign date of first dose of study drugs or medication end date (if not missing), whichever is earlier.
	Missing Day, Month	Assign Jan 01 unless the year is year of first dose of study drugs. Otherwise, assign date of first dose of study drugs or medication end date (if not missing), whichever is earlier.
	Missing Day, Month, Year	Assign date of first dose of study drugs or medication end date (if not missing), whichever is earlier.
End Date	Missing Day	Assign the last date of the month or death date or data cut-off date (or end of study date), whichever is earliest.
	Missing Day, Month	Assign Dec 31 or death date or data cut-off date (or end of study date), whichever is earliest.
	Missing Day, Month, Year	If ongoing, end date is missing. Otherwise, assign death date or data cut-off date (or end of study date), whichever is earlier.

The imputed date will be used to categorized TEAEs and prior/concomitant medications. The data listings will report original data instead as the imputed date.

For incomplete dates involving efficacy and other safety data, a conservative imputation will be used for calculation if needed. More details of imputation rules will be specified in study analysis dataset specification.

2.9 Timing of Analysis

2.9.1 Interim Analysis

In Phase 1b there is a safety interim analysis after each DL to determine the dosing for the next subject.

In Phase 2a, Arms I, II, III, IV, and V will have a futility interim analysis per the Simon's two-stage minimax design at 17 evaluable subjects based on ORR assessed by iRECIST. If at least one subject achieves objective response (iCR or iPR) in an arm, that arm may be expanded by enrolling up to 8 evaluable additional subjects in Stage 2. Study enrollment will continue while the first 17 possible evaluable subjects are undergoing evaluation to confirm response. If no objective response is observed in an arm during Stage 1, further enrollment will be stopped in that arm.

In Phase 2a, Go/No Go decision for Arms I, II, III, IV, and V will be based on iRECIST, since iRECIST assessment starts after 1st PD defined by RECIST 1.1.

An interim analysis will not be performed for IVa, Va, and the Biomarker Cohort.

2.9.2 Final Analysis

Final analysis will be performed based on the data from electronic data capture (EDC) and vendors after database lock.

3. ANALYSIS SETS

3.1 Safety Analysis Set

The safety analysis set is defined as all subjects who received at least one dose (even partially) of one or both study medications. This analysis set will be used for all safety analysis.

3.2 DLT Evaluatable Analysis Set

The DLT evaluable analysis set will consist of those subjects in Phase 1b portion of the study who are in safety analysis set and have completed the first 21 days (3 weeks) of study treatment (Cycle 1, Day 1 to 21) or any subjects who have not completed 21 days due to DLT.

3.3 Efficacy Evaluatable Analysis Set

The efficacy evaluable analysis set will include all subjects who have received at least one dose of both the study medication (NT-I7 and Pembrolizumab) and have an evaluable baseline and at least one evaluable post-baseline assessment of tumor response.

This analysis set will be used as the primary analysis set for all efficacy analysis.

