
 
To make further assessment of the anti-tumor activity of NT-I7 in combination with pembrolizumab in these patient populations based on Objective Response Rate (ORR) (for Biomarker Cohort only), Duration of Response (DoR), Disease Control Rate (DCR), Progression-Free Survival (PFS), and Overall Survival (OS) by RECIST 1.1 and iRECIST.
 
	
 
Objective Response Rate (ORR, Biomarker Cohort only) defined as the percentage of subjects who have at least one confirmed partial response (PR) or complete response (CR), per by RECIST 1.1 and iRECIST as determined by the investigator.
 
Duration of response (DoR) for the responders in each individual arm, defined as the time from the first occurrence of a documented objective response to the time of the first documented disease progression or death from any cause, whichever occurs first, per RECIST 1.1 and iRECIST as determined by the investigator.  DoR will be assessed statistically via Kaplan-Meier methods and presented descriptively for the responders. Comparative assessments are not planned on this endpoint.
 
Disease Control Rate (DCR) for each individual arm, defined as proportion of subjects with a best overall response of CR, PR or SD, per RECIST 1.1 and iRECIST as determined by the investigator.  DCR will be assessed statistically via Fisher Exact tests supported by Clopper-Pearson confidence intervals; all analyses will be interpreted descriptively. Comparative assessments are not planned on this endpoint.
 
Progression Free Survival (PFS) for each individual arm, defined as the time from the first study treatment (Cycle 1, Day 1) to the first occurrence of progression or
 

---	---

	
death from any cause, whichever occurs first, per RECIST 1.1 and iRECIST as determined by the investigator.
 
PFS will be assessed statistically via Kaplan-Meier methods and presented descriptively for all treated subjects in each study arm; censoring rules and statistical endpoint definitions (time to event) will be detailed in the SAP prospectively. Comparative assessments are not planned on this endpoint.
 
 
• Overall survival (OS) for each individual arm, defined as the time from first study treatment (Cycle 1, Day 1) to death from any cause.
 
 
OS will be assessed statistically similarly to PFS (above).

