#### **15.5. Statistical Analysis Plan Summary**

Study Design Overview	An Open-label Phase 1b/2a Study of NT-I7 (efineptakin alfa) in Combination with Pembrolizumab in Subjects with Relapsed/Refractory Advanced Solid Tumors
Analysis Populations	Safety: All-Subjects-as-Treated (ASaT) PK: Per-Protocol (PP) Efficacy: All evaluable per arm, a subset may be repeated on All-Subjects-as-Treated (ASaT).

	Descriptive analysis will be performed at the end of enrollment for Arms IVa and Va.
Primary Endpoint(s)	
Phase 1b:
 
 
Incidence, nature, and severity of adverse events graded according to NCI CTCAE v5.0
 
Incidence and nature of DLTs
 
Potential correlation of dose levels with safety and efficacy parameters
 
 
Phase 2a:
 
 
Objective Response Rate (ORR) for each individual arm, defined as the percentage of subjects who have at least one confirmed partial response (PR) or complete response (CR), per RECIST 1.1 and iRECIST as determined by the investigator
 
 
Biomarker Cohort:
 
 
To assess a potential correlation between tumor infiltrating lymphocytes (TILs) and clinical benefits in subjects with CPI-naïve R/R OC.
 

Secondary Endpoints	
Phase 1b/2a:
 
 
Duration of objective response (DOR) for each individual arm, defined as the time from the first occurrence of a documented objective response to the time of the first documented disease progression or death from any cause, whichever occurs first, per RECIST 1.1 and iRECIST as determined by the investigator.
 
Disease Control Rate (DCR) for each individual arm, defined as proportion of subjects with a best overall response of CR, PR or stable disease (SD), per RECIST 1.1 as determined by the investigator.
 
Progression Free Survival (PFS) for each individual arm, defined as the time from the first study treatment (Cycle 1, Day 1) to the first occurrence of progression or death from any cause, whichever occurs first, per RECIST 1.1 as determined by the investigator.
 
Overall survival (OS) for each individual arm, defined as the time from first study treatment (Cycle 1, Day 1) to death from any cause
 
Incidence of anti-drug antibody (ADA) to NT-I7 during the study relative to the prevalence of ADA at baseline
 

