
	
whichever occurs first, per RECIST 1.1 as determined by the investigator.
 
PFS will be assessed statistically via Kaplan-Meier methods and presented descriptively for all treated patients in each study arm; censoring rules and statistical endpoint definitions (time to event) will be detailed in the SAP prospectively. Comparative assessments are not planned on this endpoint.
 
 
Overall survival (OS) for each individual arm, is defined as the time from first study treatment (Cycle 1, Day 1) to death from any cause.
 
OS will be assessed statistically similarly to PFS (above).
 
Incidence of anti-drug antibody (ADA) to NT-I7 during the study will be assessed, relative to the prevalence of ADA at baseline. Immunogenicity to NT-I7 will be measured using a risk-based, tiered testing approach. Additional details are provided in Table 1.
 

Treatment Assignment	This is not a randomized study.
Statistical Methods for Safety Analyses	Summary statistics will be provided for the safety endpoints as appropriate.
Interim Analyses	
For Phase 2a, Arms I, II, III, IV, and V, an interim analysis for futility is included, per the Simon minimax design.
 
An interim analysis will not be performed for Arms IVa, Va, and the Biomarker Cohort Ovarian Cancer.
 
An interim analysis for Phase 1b will be performed.

Multiplicity	No multiplicity adjustment is planned.
Sample Size and Power	
Up to 238 subjects (up to 18 subjects in the Phase 1b, up to 210 subjects in the Phase 2a and up to 10 subjects in the Biomarker Cohort) are planned to be enrolled in the study.
 
This will provide an estimated 80% power per selected arm in the Phase 2a stage of the study for the primary hypothesis test using the Simon minimax design, for 4% vs 21% ORR, at 1-sided alpha = 0.025, as well as approximately 25 evaluable subjects per arms for 95% exact binomial Clopper-Pearson confidence intervals for ORR from the design (per arm).

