4.9 Efficacy Analysis

All efficacy analysis will be summarized by DL or arm for each phase primarily based on efficacy evaluable analysis set.

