4.9.1 Tumor Assessment and Overall Visit Response

Initial tumor imaging at Screening must be performed within 28 days prior to the date of treatment. The first on-study imaging assessment should be performed at 6 weeks (± 1 week) from the date of the first study treatment. Subsequent tumor imaging should be performed every 6 weeks (± 1 week) or more frequently if clinically indicated. After the first 6 months, subjects who remain on treatment will have imaging performed every 9 weeks (± 1 week). Imaging should continue to be performed until disease progression is identified by the investigator, or notification by the Sponsor, whichever occurs first.

Target lesion response, non-target lesion response, and overall response of each visit will be reported by investigator according to RECIST 1.1 criteria and iRECIST criteria in protocol Appendix A.

The RECIST 1.1 assessment has the following possible response categories: CR, PR, SD, PD or NE.

The iRECIST criteria is similar to RECIST 1.1 but requires an evaluation of PD to be confirmed at subsequent assessment. For purposes of iRECIST assessment, the first visit showing PD according to RECIST 1.1 will be assigned as immune-unconfirmed PD (iUPD) at this visit. On a subsequent confirmatory imaging, the subject will be classified as progression confirmed (with an overall response of iCPD, see protocol Appendix A for the confirmation rules for iCPD). The iRECIST assessment has the following possible response categories: iCR, iPR, immune-Stable Disease (iSD), iUPD, iCPD, and NE.

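### PFS and OS are analysed only in subjects with an evaluable post-baseline scan, so deaths before that scan drop out; the protocol's PFS text says all treated subjects, and the SAP does not record its choice.

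*SAP*

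**What the plan says.** **SAP.** Section 3.3 admits a subject to the efficacy evaluable set only with at least one dose of both drugs, an evaluable baseline and at least one evaluable post-baseline tumour assessment. It adds: "This analysis set will be used as the primary analysis set for all efficacy analysis". Section 4.9 agrees: "All efficacy analysis will be summarized by DL or arm for each phase primarily based on efficacy evaluable analysis set". Sections 4.9.4.3 and 4.9.4.4 start PFS, iPFS and OS at first dose, count death as an event for each, and name no other population. On scan timing, Section 4.9.1 says: "The first on-study imaging assessment should be performed at 6 weeks" (plus or minus one week).

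**Protocol.** Table 1 says: "PFS will be assessed statistically via Kaplan-Meier methods and presented descriptively for all treated subjects in each study arm". Section 15.5 repeats this: "PFS will be assessed statistically via Kaplan-Meier methods and presented descriptively for all treated patients in each study arm". In both places OS is to be assessed similarly to PFS. The Analysis Populations row of Section 15.5 says something different: "Efficacy: All evaluable per arm, a subset may be repeated on All-Subjects-as-Treated (ASaT". Neither document says which text prevails.

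**Record of the choice.** SAP Section 6 lists only biomarker changes. A note in Protocol 15.5 also says that exploratory analyses on all enrolled and treated subjects will be presented; the SAP specifies none for efficacy.

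**The concern.** The clock starts at first dose, but entry to the analysis set depends on something that happens later. A subject who dies before any evaluable scan contributes neither an event nor time at risk, and nobody in the set can die before that scan. This is selection on survival, and for these deaths it always works in the favourable direction. They are among the earliest events, so the whole later part of each curve is raised.

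The case for the restriction is weakest for OS, which needs no scan. In single-arm cohorts with no planned comparison, the descriptive curves and medians are the whole PFS and OS result, and readers will set them beside outside figures. SAP Section 5 carries the same set into the interim Kaplan-Meier plots.

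**Working it through.** **The plan's own figure.** No sizing figure is given for PFS or OS. The only one is 80% power for ORR, 4% versus 21%, with 17 then 25 evaluable subjects at one-sided alpha 0.025 (Protocol 15.1). An exact two-stage binomial calculation, stopping at 0 of 17 and rejecting at 4 or more of 25 (the final cut-off is not stated; this is the one that fits), gives power 0.8001 and attained alpha 0.0164. The figure reproduces and does not depend on the PFS/OS population.

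**Inputs from the documents**
- Up to 30 enrolled for 25 evaluable per arm (Protocol 15.1), a gap of 5 that covers non-evaluable subjects and dropouts.
- First scheduled scan at week 6 (SAP 4.9.1).
- Life expectancy of at least 12 weeks at entry (Protocol 4.1, criterion 7).

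**Assumptions (not in the documents)**
- *k* of 30 treated subjects die before a scan, with *k* = 1, 2, 3 or 5.
- In the evaluable set, 6-month (26-week) OS is 50%, median OS is 26 weeks and 3-month PFS is 30%.

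**Formula.** For any time *t* after the first scan, S_all(t) = ((30 − k)/30) × S_eval(t). For the median, let deaths in the evaluable set be exponential from week 6 with median 26 weeks, so S_eval(t) = 2^(−(t − 6)/20). Setting S_all(t) = 0.5 gives t = 6 + 20 × (1 + log2((30 − k)/30)).

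| k of 30 | (30 − k)/30 | 26-week OS, from 50% | Median OS, from 26 weeks | 3-month PFS, from 30% |
|---|---|---|---|---|
| 1 | 0.967 | 48.3% | 25.0 weeks | 29.0% |
| 2 | 0.933 | 46.7% | 24.0 weeks | 28.0% |
| 3 | 0.900 | 45.0% | 23.0 weeks | 27.0% |
| 5 | 0.833 | 41.7% | 20.7 weeks | 25.0% |

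**Checks**
- A simulation of 20,000 runs, with the *k* deaths uniform over weeks 0 to 6, agrees to within 0.1 percentage point and 0.1 week. It shares the assumptions above, so it checks only the arithmetic.
- The median depends on the assumed curve. With exponential survival from first dose and an evaluable median of 6.0 months, 6.0 × (1 + log2((30 − k)/30)) gives 5.7, 5.1 and 4.4 months for k = 1, 3 and 5.
- If 5 of 30 have no scan, *k* of them die and the rest are censored at Day 1, 3-month PFS is 30% × 25/(25 + k) = 28.8%, 27.8%, 26.8% and 25.0% for k = 1, 2, 3 and 5. The result is nearly the same.

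**The case against.** The SAP follows the row of the protocol that is headed Analysis Populations, so it can be argued that there is no change to record in Section 6. For OS, being assessed similarly to PFS may mean only that Kaplan-Meier methods are used. This stands in part: the SAP does not contradict every protocol passage, and all-treated OS is implied rather than stated. But the only sentences specific to PFS say all treated, and a conflict settled without comment still needs a written resolution.

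Early deaths are not hidden. SAP 4.1 reports the size of both sets, and SAP 4.11.2 tabulates adverse events leading to death on the safety set. A reader can therefore learn that such deaths occurred, but not what they do to the curves.

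Fewer subjects may be lost than the week-6 date suggests. Protocol 7.4 (footnote 16) allows earlier imaging if clinically indicated, and Protocol 13.3 asks for imaging when treatment stops. Only subjects with no evaluable scan at all are left out.

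The upper end of the range is doubtful. Protocol 2.3 reports 27 and 26 evaluable subjects in the completed Arms IV and V. If the cap of 30 held and evaluable meant the same there, at most 3 and 4 were non-evaluable for any reason, so k = 5 could not occur in those arms. The 30 is also an enrolment figure, not a count of treated subjects.

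At k = 1 or 2 the OS shift is 1.7 to 3.3 points, small beside a standard error of about 9 points for a 50% proportion in 30 subjects (√(0.25/30) = 0.091). That is fair as to size, but this bias has a known direction and is avoidable without new data.

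**Conclusion.** The concern holds. As written, the SAP analyses PFS, iPFS and OS in a set that leaves out treated subjects who die before an evaluable scan, and it adopts that set without noting that the protocol gives two answers. The direction for those deaths is certain; the size cannot be found from the documents. On the assumptions above, a 50% 6-month OS is overstated by 1.7 points at one such death in 30 and by 8.3 points at five. Five is an extreme that treats the whole enrolment allowance as deaths before a scan, and the 12-week life-expectancy criterion makes the low end more likely. The consequence is limited to secondary, descriptive endpoints; the primary ORR test and the Go/No Go decision do not change. The point should be fixed before the analysis.

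**What to change.** - **SAP 3.3, 4.9.4.3 and 4.9.4.4:** name the Safety Analysis Set ("all subjects who received at least one dose (even partially) of one or both study medications") as primary for PFS, iPFS and OS, with the evaluable set as a sensitivity analysis. This set includes subjects who received only one drug, so say so.
- **Events and censoring:** count a death before any post-baseline scan as an event, subject for PFS and iPFS to the existing rule on two or more missed assessments in SAP Tables 4 and 5. Censor subjects with neither a post-baseline scan nor a death at Day 1 for PFS and iPFS, and at the last known alive date for OS.
- **ORR and iORR:** leave the primary test on evaluable subjects, and add the exploratory all-treated analysis promised in the note to Protocol 15.5.
- **SAP Section 6:** state how the conflict between the Analysis Populations row and the PFS text in Protocol Table 1 and Section 15.5 was resolved. If the sponsor keeps the evaluable set for PFS and OS, give the reason there.

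The cost is a few sentences and one extra set of tables, with no new data. PFS and OS may look slightly less favourable.

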3.4 Per-Protocol (PP) Analysis Set

The PP analysis set is defined as all subjects who received at least one dose of both study medication (NT-I7 and Pembrolizumab), had at least one serum concentration, and did not have any important protocol deviations that potentially affect NT-I7 and Pembrolizumab metabolism.

The PP Set will be used for all PK analysis.

4. STATISTICAL METHODOLOGY

4.1 Study Subjects Disposition

Following information will be provided.

- Number of subjects screened and enrolled study
- Safety analysis set,

Confidential

- DLT evaluable analysis set
- Efficacy evaluable analysis set
- Per Protocol (PP) analysis set
- Number and percentage of subjects who completed treatment
- Number and percentage of subjects who discontinued treatment
- Primary reason for discontinuation of treatment: Include the reasons being reported in EDC only. It will be categorized as ‘Missing’ if the reason is missing due to data issue.
 - AE
 - Dead
 - Lack of efficacy
 - Lost to follow-up
 - No longer clinically benefiting
 - Non-compliance with study schedule
 - Physician decision
 - Pregnancy
 - PD
 - Protocol deviation
 - Protocol-specified withdrawal criterion met
 - Recurrent disease
 - Study terminated by sponsor
 - Subject removed at sponsor request
 - Technical problem
 - Trial site terminated by sponsor
 - Withdrawal by subject
 - Other
- Number and percentage of subjects who completed the study
- Number and percentage of subjects who discontinued the study
- Primary reason for study discontinuation: Include the reasons being reported in EDC only. It will be categorized as ‘Missing’ if the reason is missing due to data issue.
 - AE
 - Dead
 - Lack of efficacy
 - Lost to follow-up
 - No longer clinically benefiting
 - Non-compliance with study schedule
 - Physician decision
 - Pregnancy
 - PD
 - Protocol deviation
 - Protocol-specified withdrawal criterion met
 - Recurrent disease
 - Study terminated by sponsor
 - Subject removed at sponsor request

- Technical problem
- Trial site terminated by sponsor
- Withdrawal by subject
- Other

Subjects disposition data will also be presented in data listings.

